7.2 Demographic/Medical History and Baseline Assessments

The following demographic parameters will be captured during Screening: date of birth, gender, race and ethnicity.

Medical/medication history assessed as related to the eligibility criteria listed in [Section 5.2](#).

Baseline (Screening) assessments are detailed in the Time and Events Table [Section 7.1](#).

Procedures conducted as part of the subject's routine clinical management (e.g., blood count, imaging study) and obtained prior to signing of informed consent may be utilized for Screening or baseline purposes provided the procedure meets the protocol-defined criteria and has been performed in the timeframe of the study.

Additional historic data will be collected, if available, on patients with a diagnosis of LGG enrolled in all study parts. The additional data will consist of efficacy assessments (imaging scans, primarily MRI) from the most recent prior chemotherapy regimen to include the baseline assessment (scan taken just before the initiation of the prior chemotherapy) and a time point closest to 6 months following initiation of that therapy.

7.3 Safety Evaluations

Planned time points for all safety assessments are provided in the Time and Events Table ([Section 7.1](#)).

7.3.1 Physical Examinations

A complete physical examination will include assessments of the head, neck, eyes, ears, nose, mouth, throat, skin, thyroid, neurological, lungs, cardiovascular, abdomen (liver and spleen), lymph nodes and extremities. Height and weight will also be measured and recorded. Sexual maturation will be assessed using Tanner staging.

A brief physical examination will include assessments of the head, neck, eyes, skin, lungs, cardiovascular system, and abdomen (liver and spleen).

A full body dermatological examination will be performed by a dermatologist (or suitably qualified physician) to identify abnormal skin lesions. All findings will be photographed and identified during screening. Brief skin examinations will be performed as indicated in the Time and Events Table or more frequently as necessitated. Wherever possible, the same physician should perform these examinations. Follow-up skin examinations by a referral dermatologist should be conducted if clinically indicated.

Plain radiographs of the wrist or tibial growth plates (following institutional practice) are required in children with open growth plates at Day 1. Radiograph can be performed anytime between screening and Day 1.

7.3.2 Ophthalmology Examination

An age-appropriate ophthalmologic examination should be performed by an ophthalmologist at screening and at the timepoints specified in the Time and Events Tables ([Section 7.1](#)).

During the study, ophthalmologic exams may be repeated as clinically warranted. If any changes are noted during the required age-appropriate exam, or otherwise clinically indicated, a detailed ophthalmologic exam is mandatory (with sedation if necessary).

7.3.3 Performance Status

The performance status will be assessed using Karnofsky and Lansky Scales (Appendix 1) as specified in the Time and Events Table ([Section 7.1](#)).

7.3.4 Vital Signs

Vital sign measurements will include systolic and diastolic blood pressure, temperature, respiration rate and pulse rate. Vital signs should be measured after resting for at least 5 minutes in a semi-supine position. Vital signs will be measured more frequently if warranted by clinical condition of the subject. On days where vital signs are measured multiple times, temperature does not need to be repeated unless clinically indicated. Refer to the SPM for details regarding measurement of vital signs. Baseline blood pressure measurement should be performed in triplicate and for all other occasions, measurement should be performed once.

Baseline blood pressure (BP) is defined as the blood pressure obtained at the examination used for study enrollment. This baseline BP should be obtained as follows:

1. Obtain 3 serial blood pressures from the same extremity with the patient in the same position that are separated by at least 5 minutes. Avoid using the lower extremity if possible.
2. Average the systolic blood pressure from the 2nd and 3rd measurements.
3. Average the diastolic blood pressure from the 2nd and 3rd measurements.
4. The baseline BP is the average of the systolic and average of the diastolic measurements.

7.3.5 Electrocardiogram

Single 12-lead ECGs will be obtained at designated time points during the study using an ECG machine that automatically calculates the heart rate and measures PR interval, QRS, QT, and corrected QT (QTc) intervals. At each assessment a 12-lead ECG will be performed by qualified personnel at the site after the subject has at least a 10 minute rest.

The QT interval should be corrected for heart rate by Bazett's formula (QTcB). Refer to [Section 3.12.1](#) for QTc stopping criteria. Additional QTc readings may be performed if necessary. Refer to the SPM for details regarding ECG procedures.

7.3.6 Echocardiogram

The ECHOs will be performed to assess cardiac ejection fraction and cardiac valve morphology for the purpose of study eligibility and during the study as specified in the Time and Events

Table (Section 7.1). Additional ECHO assessments may be performed if clinically warranted. The evaluation of the echocardiographer should include an evaluation for LVEF and both right and left-sided valvular lesions.

Copies of all study ECHOs performed will be required to be provided to the sponsor. The ECHOs will not be reviewed in a real-time basis by the sponsor, but rather held for review at a future time point if a cardiac safety signal is identified.

7.3.7 Laboratory Assessments

All protocol required laboratory assessments, as defined in Table 7-6, should be performed according to the Time and Events Table (Section 7.1). Details for the preparation and shipment of samples will be provided in the SPM.

Prior to administration of the first dose of study treatment, results of laboratory assessments should be reviewed. Any laboratory test with a value outside the normal range may be repeated (prior to the first dose) at the discretion of the investigator.

If additional non-protocol specified laboratory assessments are performed at the institution's local laboratory and result in a change in subject management or are considered clinical significant by the investigator (for example SAE or AE or dose modification) the results must be recorded in the subject's CRF. Refer to the SPM for appropriate processing and handling of samples to avoid duplicate and/or additional blood draws.

All laboratory tests with values that are significantly abnormal (Grade ≥ 3) during participation in the study or within 30 days after the last dose of study treatment should be repeated until the values return to normal or baseline. If such values do not return to normal within a period judged reasonable by the investigator, the etiology should be identified and the sponsor notified.

Hematology, clinical chemistry, urinalysis and additional parameters to be tested are listed below:

Table 7-6 List of Clinical Laboratory Tests

Hematology			
Platelet Count		RBC Indices:	Automated WBC Differential:
Red blood cell (RBC) Count		MCV	Neutrophils
White blood cell (WBC) Count (absolute)		MCH	Lymphocytes
Hemoglobin		MCHC	Monocytes
Hematocrit			Eosinophils
HbA1c at baseline (screening) only			Basophils
Clinical Chemistry			
Blood urea nitrogen (BUN)	Potassium	Aspartate aminotransferase (AST)	Total and direct bilirubin (Bilirubin fractionation recommended if total bilirubin is >2x the upper limit of normal)
Creatinine	Chloride	Alanine aminotransferase (ALT)	Total Protein
Glucose (recheck fasting if >160 mg/dL)	Total carbon dioxide (CO ₂)	Gamma glutamyl transferase (GGT)	Albumin
Sodium	Calcium	Alkaline phosphatase (ALP)	
Magnesium	Phosphate		
Routine Urinalysis			
Specific gravity			
pH, glucose, protein, blood and ketones by dipstick			
Microscopic examination (if blood or protein is abnormal)			
Other screening tests			
Serum pregnancy test			
HVA/VMA in random or 24 hr urine for subjects with neuroblastoma			
In the event of abdominal pain or suspected pancreatitis, amylase and lipase laboratory samples should be collected.			

RBC = Red Blood Cell; WBC = White Blood Cell; MCV = Mean Corpuscular Volume; MCH = Mean Corpuscular Hemoglobin; MCHC = Mean Corpuscular Hemoglobin Concentration; HVA/VMA = Homovanillic Acid / Vanillylmandelic Acid (ratio); CSF = Cerebrospinal fluid.

Palatability

For subjects ≥12 years of age who receive the dabrafenib suspension or trametinib oral solution, the subject will complete a form (for each drug separately if enrolled in Parts C and D) to evaluate the various properties of the suspension (e.g., bitterness, sweetness, appearance, texture and overall taste). If the subject ≥12 years of age needs assistance completing the questionnaire(s), his/her caregiver (e.g. parent or guardian) will be requested to evaluate the suspension with the child based on verbal and non-verbal feedback. For subjects <12 years of age who receive the suspension, their caregiver (e.g. parent or guardian) will be requested to evaluate the suspension with the child based on verbal and non-verbal feedback. Questionnaires for trametinib and dabrafenib are provided in the SPM. The questionnaire (s) may be completed after the first dose of study drug (s) and must be completed no later than Day 8 (±3 days).

7.3.8 Pregnancy Testing and Reporting

The need for a screening pregnancy test depends on whether a female subject is of childbearing potential or non-childbearing potential.

If a female subject is of childbearing potential, she must have a serum β -Human Chorionic Gonadotropin (β -HCG) pregnancy test performed within 7 days prior to the first dose of study treatment(s). Subjects with a positive pregnancy test result must be excluded from the study. Subjects with a negative pregnancy test result must agree to use an effective contraception method as described below during the study until 4 months following the last dose of study treatment(s).

Any pregnancy that occurs during study participation must be reported using a clinical trial pregnancy form. To ensure subject safety, each pregnancy must be reported to Novartis within 24 hours of learning of its occurrence. The pregnancy must be followed up to determine outcome (including premature termination) and status of mother and child. Pregnancy complications and elective terminations for medical reasons must be reported as an AE or SAE. Spontaneous abortions must be reported as an SAE.

Any SAE occurring in association with a pregnancy brought to the investigator's attention after the subject has completed the study and considered by the investigator as possibly related to the study treatment(s), must be promptly reported to Novartis.

In addition, the investigator must attempt to collect pregnancy information on any female partners of male study subjects who become pregnant while the subject is enrolled in the study. Pregnancy information must be reported to Novartis as described above.

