6.2 Subject Completion Criteria

A subject will be considered to have completed the study if they discontinued study treatment for reasons listed in [Section 6.2](#) and completed a post-treatment follow-up visit or has died while receiving study treatment.

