6.6 Treatment after the End of the Study

The investigator is responsible for ensuring that consideration has been given for the post-study care of the subject's medical condition whether or not Novartis is providing specific post-study treatment.

After study participation in the current study is completed or terminated, subjects may either:

1. Transition to the rollover study if eligible and continue receiving treatment with trametinib or trametinib and dabrafenib

OR

2. Complete a follow-up visit after the last dose of study treatment(s) if the subject:
 - chooses not to enter the roll-over study, or
 - is withdrawn due to an AE considered related to study treatment, or
 - is considered ineligible to enter the rollover study.

Subjects who discontinued treatment with trametinib or dabrafenib will be offered Follow-Up from Novartis consisting of a visit every 3 months (± 15 days) for a period of 2 years. At each visit, the following assessments will be performed:

- Brief history and physical exam (a brief physical examination will include assessments of the skin, lungs, cardiovascular system, and abdomen (liver and spleen) [and neurological exam as clinically indicated]; brief physical exam to also include dermatologic evaluation, growth, and sexual maturation);
- History to review development;
- History of new malignancies or secondary malignancies, or other significant changes.

Subjects who discontinued dabrafenib treatment will be followed every 3 months for 2 years to monitor for the occurrence of cuSCC and monitored for up to 2 years for non-cutaneous malignancy.

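### Mandatory pregnancy reporting is tied to study participation and can end before the 4-month contraception period does (Protocol 7.3.8)

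*Protocol*

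**What the plan says.** Section 7.3.8 sets three rules with different time limits.

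- **Contraception:** a female subject of childbearing potential must use it during the study and "until 4 months following the last dose of study treatment(s"). Sections 10.1.1 and 10.1.2 give 16 weeks after trametinib (females) and after study treatment (males).
- **Notification and outcome follow-up:** "Any pregnancy that occurs during study participation must be reported using a clinical trial pregnancy form", within 24 hours, with follow-up of the outcome and of mother and child. For male subjects, the investigator must try to collect information on partners "who become pregnant while the subject is enrolled in the study".
- **After completion:** what remains is any serious adverse event associated with a pregnancy that comes to light "after the subject has completed the study and considered by the investigator as possibly related to the study treatment(s), must be promptly reported".

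The end of participation has to be pieced together from other sections. Section 6.2 counts a subject as having completed the study after stopping treatment if the subject has "completed a post-treatment follow-up visit or has died while receiving study treatment". Section 6.6 begins "After study participation in the current study is completed or terminated, subjects may either", and one of the options it then lists is a follow-up visit. It adds that subjects who stopped treatment "will be offered Follow-Up from Novartis consisting of a visit every 3 months", for 2 years. Section 7.3.7 speaks of abnormal values "during participation in the study or within 30 days after the last dose of study treatment", which names the 30 days separately from participation.

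Inclusion criterion 6 in 5.2.1.1 also expects negative pregnancy tests for 4 months after the last dose.

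**The concern.** The contraception rule marks a post-dose period in which the protocol regards pregnancy as a risk. Section 1.7.1 gives the reason for trametinib (developmental toxicity in animals below clinical exposure), and section 1.7.2 for dabrafenib (embryo-lethality and ventricular septal defects in rats). A pregnancy in that period is the event the rule is meant to prevent, so it is one whose outcome the sponsor would want to know.

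The reporting trigger does not use that period. If participation ends early, a subject or partner pregnancy conceived later in the window, with no serious adverse event judged possibly related, needs neither notification nor outcome follow-up. Sites may also place the end of participation differently, so exposed pregnancies would be collected unevenly.

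**Working it through.** No statistical figure is involved. The check is a comparison of the sections and a subtraction of windows.

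**Inputs**
- Contraception window: 16 weeks = 16 × 7 = 112 days (10.1.1, 10.1.2); 4 months taken as about 122 days (7.3.8).
- Final-visit assessments: any time from the last dose to 30 days after it (6.3).
- Follow-up visits: every 3 months ± 15 days (6.6). Taking 3 months as about 91 days and assuming the clock starts at the last dose, which 6.6 does not state, the first visit is at 91 ± 15 = day 76 to 106 and the second at 182 ± 15 = day 167 to 197.

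**Uncovered days = window length − day on which participation ends**

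| Participation ends at | 16 weeks (112 days) | 4 months (about 122 days) |
|---|---|---|
| Final visit, day 0–30 | 112 − 30 = 82 to 112 − 0 = 112 | 122 − 30 = 92 to 122 − 0 = 122 |
| First 3-monthly visit, day 76–106 | 112 − 106 = 6 to 112 − 76 = 36 | 122 − 106 = 16 to 122 − 76 = 46 |
| End of all 6.6 follow-up (2 years) | 0 | 0 |

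**Which row applies?** The text does not settle it.
- For the first row: 6.6 places its follow-up visit after participation has ended, and 7.3.7 separates the 30 post-dose days from participation.
- For the second row: 6.2 requires a post-treatment follow-up visit. Section 6.3 sends the reader to the Time and Events Table for post-treatment follow-up, and Table 7-4 points on to 6.6, where the dated visits are 3-monthly.
- For the third row: no sentence says that the 6.6 follow-up counts as participation. It is offered to subjects who stop treatment, and stated as something that will happen only for those who stopped dabrafenib.
- Section 6.2 cannot decide the matter. It cites itself for the discontinuation reasons, which are in 6.3, and gives its visit no date.

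**Do other provisions cover the remaining days?**
- Section 8.4 collects adverse events to 30 days. After that the investigator may report possibly related events but is not obliged to.
- Section 8.4.2 and Table 8-1 set a 24-hour clock for pregnancies and state no post-dose period.
- Inclusion criterion 6 expects tests to 4 months, but Table 7-4 schedules pregnancy tests only to the final visit, and the 6.6 list has no pregnancy item. Its open history item on other significant changes might bring a pregnancy out. The criterion concerns female subjects only.

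**Who can still be affected?** Amendment 9 reports 139 treated, 80 off treatment and 13 in the rollover study. On treatment in this study: 139 − 80 = 59 if the 13 are among the 80, or 139 − 80 − 13 = 46 if they are not. Some of the 80 may still be inside the window; that number is not given. Nor is the number able to become pregnant or father a child.

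**The case against.** The strongest reply is that the protocol is not silent. A reader might infer from 7.3.8 alone that the end of participation is nowhere defined. That goes too far: 6.2 defines completion, 8.4 refers to Section 6 for it, and 7.3.8 itself uses the idea of having completed the study. What stands is narrower: the definition is undated, cites itself and sits awkwardly beside 6.6.

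A reader might also take the gap to be nearly the whole window. That is one reading only. If the visit in 6.2 is the first 3-monthly visit, most of the window is covered.

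Nor do the documents support saying that late pregnancies would simply go undetected. Inclusion criterion 6 expects testing over the same 4 months, possibly related serious events stay reportable, and follow-up visits take an open history. These soften the gap but create no duty to notify or follow an uncomplicated pregnancy, and the testing does not reach partners.

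Table 8-1 could be read as having no time limit, since it gives none. However, 8.4.2 applies once an event meets the protocol's definition of it, and for pregnancy the only stated trigger is in 7.3.8. The table therefore does not clearly extend the duty.

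Finally, enrolment is closed and 80 subjects had already stopped treatment. That limits the benefit of a change but does not remove it.

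**Conclusion.** The point holds as a mismatch between two windows in one section. Unless the whole 6.6 follow-up counts as participation, part of the protocol's own contraception period lies outside mandatory pregnancy notification and outcome follow-up: from 6 days at the least (first 3-monthly visit, 16-week window) to about 122 at the most (final visit on the last-dose day, 4-month window). The sizes assume 122 days for 4 months, 91 days for 3 months, and follow-up visits counted from the last dose.

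It is a minor matter of safety reporting. The documents give no basis for estimating how many pregnancies are at issue, and nothing in the efficacy, dose-finding or pharmacokinetic results depends on it. The 139 treated subjects are not the number affected: an amendment could reach only those still on treatment (46 to 59 at the Amendment 9 count) and any still inside the window. Subjects in the rollover study continue treatment there and are not described by these figures.

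**What to change.** In 7.3.8, give the subject and partner triggers the same wording: *from first dose, throughout study participation, and in any case until at least 4 months after the last dose of study treatment*. It should be phrased as a minimum. Replacing participation outright with 4 months could shorten reporting for anyone who counts the 2-year follow-up as participation.

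Add one question on subject or partner pregnancy at the first existing 6.6 contact after the window closes, by telephone if the subject declines visits. Counting from the last dose, that is the second 3-monthly visit (about day 167 to 197), because the first (about day 76 to 106) comes too early.

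The cost is a minor amendment and one added question, using the existing pregnancy form. For female subjects the question partly overlaps with the testing expected under inclusion criterion 6.

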7.4 Pharmacokinetics

PK parameters for study treatment (trametinib, dabrafenib and its metabolites) for subjects in whom the full blood sampling scheme will be used will be calculated with standard non-compartmental methods. The PK parameters calculated with non-compartmental methods include: AUC(0-t), C_{max}, T_{max}, C _{τ} , CL/F, and AUC (0- τ) (where τ = 24 hr for trametinib and 12 hr for dabrafenib). For subjects in whom the sparse blood sample collection scheme will be used, AUC(0- τ) and the average steady-state concentration may be estimated with a population PK model. Final PK parameters will be summarized and will be compared to historical adult data.

All trametinib and dabrafenib concentration-time data may be combined and included in a population PK analysis that will examine the influence of demographics (especially age and weight) on the PK of study treatment. Trametinib and dabrafenib PK parameters estimated in the population PK analysis may include: apparent clearance following oral dosing (CL/F), volume of distribution (V/F), and absorption rate (k_a) (trametinib only). Data may be pooled with trametinib and/or dabrafenib PK data from all parts of this study and with adult data.

7.4.1 Blood Sample Collection for Pharmacokinetics

Parts A and B:

Blood samples for PK analysis of trametinib will be collected at the time points indicated in the Time and Events Table, [Section 7.1](#). The actual date and time of each blood sample collection will be recorded. The timing of PK samples may be altered to ensure thorough PK monitoring (but the total number of samples and total blood volume collected will not change).

Parts C and D:

Blood samples for PK analysis of trametinib, dabrafenib and its metabolites, hydroxy-dabrafenib, carboxy-dabrafenib, and desmethyl-dabrafenib (GSK2285403, GSK2298683 and GSK2167542, respectively), will be collected at the time points indicated in Time and Events Table, [Section 7.1](#). The actual date and time of each blood sample collection will be recorded. The timing of PK samples may be altered to ensure thorough PK monitoring (but the total number of samples and total blood volume collected will not change).

Liver events and visual changes:

For subjects meeting any of the liver chemistry stopping criteria in [Section 3.12.1](#), blood sample for PK analysis should be drawn as close as possible to the time of the event or within 20 days of the last dose of study treatment(s). Record the date and time of the PK blood sample draw and the date and time of the last dose of study treatment(s) prior the blood sample draw on the eCRF. If the date or time of the last dose is unclear, provide the subject's best approximation. If the date or time of the last dose cannot be approximated, or if a PK sample cannot be collected within the 20-day period following the last dose, do not obtain a PK sample.

For events of visual changes (regardless of severity) for which an ophthalmic examination is conducted, a blood sample for PK analysis must be drawn as close as possible to the time of the event.

